2.0 OBJECTIVES AND SCIENTIFIC AIMS

2.1 Primary objective:

To identify the maximum tolerated dose (MTD) of stereotactic body radiotherapy (SBRT) in locally advanced pancreatic cancer (LAPC) patients who have not developed distant progression after following induction chemotherapy (FOLFIRINOX or gemcitabine and nab-paclitaxel as per standard of care).

2.2 Secondary objectives:

- 1) To preliminarily assess the 2 year local control, progression free and overall survival rates for LAPC patients after induction chemotherapy and SBRT. Patterns of failure will also be investigated.
- 2) To identify early changes in the normal small intestine after SBRT for LAPC using Perfusion CT derived parameters to document changes in tissue perfusion kinetics and heterogeneity that predict for development of gastrointestinal toxicity such as duodenal ulcers, strictures, or enteritis.
- 3) To investigate vascular and cellular changes resulting from SBRT for LAPC using perfusion CT derived parameters that can predict treatment response and to assess any correlation between these perfusion CT derived parameters and local control and progression-free survival
- 4) Evaluate Quality of Life (QOL) in terms of global QOL, physical symptoms, physical functioning and emotional well-being after induction chemotherapy and SBRT. Testing will be prior to SBRT, 10-12 weeks after SBRT and 6 months after SBRT.

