15.0 BIOSTATISTICS

15.1 Dose Escalation Study and Clinical Outcomes Analysis

The primary objective of this trial is to determine the maximum tolerated dose (MTD) of SBRT after at least 3 months of induction chemotherapy for patients with LAPC. Dose limiting toxicities (DLT) are defined by \geq Grade 3 treatment-related GI toxicity within 3 months of SBRT. These include: (1) Bowel (includes bowel perforation, obstruction, or hemorrhage) and (2) Stomach (bleeding ulcer, perforation). We will employ a modified 3+3 dose-escalation scheme.

Dose escalation will be evaluated after 3 evaluable patients who have completed 90 days of follow-up. Due to dropout during the 90-day follow-up period, up to 6 patients may be accrued at each dose level to yield a cohort of at least 3 evaluable patients. The dose level will be escalated if none of the evaluable patients followed for 90 days exhibits any DLT within 90 days of completion of SBRT. If a DLT is observed in one patient, an additional cohort of patients will be treated at that dose to achieve having at least 6 evaluable patients at that dose level. The dose will be escalated if none of the additional patients exhibits any DLT (i.e. at most 1 DLT is observed at that dose level). Dose-escalation stops and the previous dose will be considered the MTD if 2 or more patients have a DLT. If the previous dose level has been administered to fewer than 6 patients, an additional cohort of patients will be enrolled to achieve having at least 6 evaluable patients at that dose level. If at most 1 DLT is observed among all evaluable patients treated at that dose level, that dose level will be declared to be the maximum tolerated dose (MTD). If, however, there are a total of 2 or more DLTs, the dose will be de-escalated again. The MTD will be the greatest dose at which at least 6 evaluable patients are treated with at most 1 of them experiencing a DLT.

If 3 patients have completed the 90 day follow-up without a DLT and there have been more patients accrued at that dose level, the dose may be escalated based on 0 DLTs among the first 3 evaluable patients. However, if one of the additional patients treated at the lower dose subsequently experiences a DLT, the dose escalation will halt. At that point accrual will continue at the lower

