dose level to achieve a total of 6 evaluable patients who have completed the 90 day follow up at the lower dose; if at most 1 of all patients at that dose level experienced a DLT then dose escalation occur and accrual at the higher dose level will resume. If 2 or more patients have a DLT at that level, the previous dose will be considered the MTD (as described above).

For this design, the probability of escalation is as follows:

True toxicity rate	5%	10%	15%	20%	25%	30%	40%	50%
Probability of escalation	0.97	0.91	0.81	0.71	0.60	0.49	0.31	0.17

Dose escalation will start with dose level 1 (9 Gy x 3 fractions) and increase by 1 Gy per fraction at each dose level, dose level 2 will be 10 Gy x 3 fractions and dose level 3 will be 11 Gy x 3 fractions. The maximum number of patients needed for this dose escalation design is 18. A patient must be successfully treated according to prescription dose before he/she can be evaluated for the safety point, otherwise he/she will be replaced by a new patient. We expect to finish the enrollment (up to 18 patients) within 3 years. All toxicity profiles will be summarized and tabulated by dose level.

For the first secondary objective, the 2 year local control (LC) rate, progression free-survival (PFS), overall survival (OS) and patterns of failure for LAPC patients after induction chemotherapy and SBRT will be assessed using survival analysis tools such as Kaplan-Meier method or cumulative incidence curves if competing risks exist. To provide some simple comparison to the historical efficacy rates we will focus on OS due to its simplicity. The historical 2-year OS rate is approximately 20% and we expect to improve it to 40% by using the proposed treatment modality. Thus we expect that, out of the 22 patients at MTD level, we shall have at least 8 patients surviving beyond 2 years. Under the null hypothesis of 20%, the probability of observing at least 8 patients surviving beyond 2 years (i.e., type I error rate) is 5.6%. Due to the small sample size and lack of power, we will not use “at least 8 patients (out of 22) surviving beyond 2 years” as a formal decision rule for declaring the success of this study. The anticipation of at least 8 patients (out of 22) surviving beyond 2 years is merely to provide us a preliminary estimation of the efficacy signal relative to the historical control in this population.

For the above efficacy secondary objective, patients at different dose levels will be examined separately.

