For the two secondary objectives involving pCT parameters (see Section 12 for details of how to obtain these parameters), all relative changes (i.e., percentage of change from the baseline, note that there will be two sets of changes, one based on the 90-minute CT and the other the 6-week CT) will be computed and correlated with the toxicity and response at

6 months post-SBRT by logistic regression. For correlation with OS, LC and PFS, survival analysis tools such as Cox model or Fine-Gray competing risks regression model will be used. For these two objectives all patients will be combined for statistical analyses.

For the QOL objective, patients will be assessed at the following time points: within 14 days prior to SBRT (Time 0); 10 to 12 weeks after SBRT (Time 1), and 6 months after SBRT (Time 2). Questionnaires will be administered in the clinic or by e-mail at all assessments. The quality of life assessment will include quality of life measures (EORTC QLQ-C30 Quality of Life Questionnaire) and the Pancreatic Cancer subscale (EORTC-PAN26). See Section 12 for more details about the quantification of the answers. The time required to complete the assessment is 20 minutes. Analysis of the QOL outcomes will be descriptive. Summary statistics will be used to characterize the patient's experience of treatment. Means, standard deviations, medians, and ranges of the QOL endpoints (scales and subscales) will be tabulated by dose level and by assessed time.

For the last secondary objective, we will assess the feasibility of obtaining adequate cytology samples for next generation sequencing using sample proportion (the number of patients who yielded sufficient material for next generation sequencing at any three time points divided by the number of patients who went through the procedure) and its confidence intervals. All patients will be combined for this objective.

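### Section 15.1 examines 2-year LC, PFS, OS and patterns of failure by dose level (about 3-6 patients each) and describes no pooled estimate; a pooled one would be more precise, though still rough

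*Combined protocol and SAP*

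**What the plan says.** The first secondary objective (Section 2.2, repeated in 13.2.1) is "To preliminarily assess the 2 year local control, progression free and overall survival rates for LAPC patients after induction chemotherapy and SBRT". The population is LAPC patients treated this way, and no dose level is named.

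Section 15.1 assigns Kaplan-Meier or cumulative-incidence methods to these endpoints and then states: "For the above efficacy secondary objective, patients at different dose levels will be examined separately". No estimate over all levels is described, and no confidence interval is specified for the 2-year rates.

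For the two perfusion-CT objectives, the same section says the opposite: "For these two objectives all patients will be combined for statistical analyses". It also combines all patients for the sequencing-feasibility objective.

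On size, Section 15.1 says "The maximum number of patients needed for this dose escalation design is 18". Level 1 is 9 Gy x 3, and "dose level 2 will be 10 Gy x 3 fractions and dose level 3 will be 11 Gy x 3 fractions". Within a level, "up to 6 patients may be accrued at each dose level to yield a cohort of at least 3 evaluable patients". For the selected dose, "The MTD will be the greatest dose at which at least 6 evaluable patients are treated with at most 1 of them experiencing a DLT".

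The overall-survival benchmark uses another figure: "out of the 22 patients at MTD level, we shall have at least 8 patients surviving beyond 2 years". It is set against a historical 2-year rate of about 20% and a hoped-for 40%.

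**The concern.** The objective asks for one set of 2-year rates, and the analysis text delivers up to three sets with no overall figure. Split by level, each rate rests on a handful of patients. Patterns of failure are thinner still, because local, distant and combined failure must share those same few patients.

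At stake is whether the trial's preliminary efficacy summary says anything. Followed literally, the report would hold several rates whose intervals run over most of the range from 0 to 100%, and would leave out the one summary the design can estimate with somewhat better precision. The by-level plan would be easier to defend if the MTD level really held 22 patients, but no part of the design provides them.

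**Working it through.** **1. The plan's own figure.** With X ~ Binomial(22, 0.20), P(X >= 8) = 0.056, which matches the stated 5.6%. With a true rate of 0.40, P(X >= 8) = 0.710. The calculation is right for n = 22; what is in doubt is whether 22 can occur.

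**2. Patients per level.** There are three levels and at most 18 patients in total. A level needs at least 3 evaluable patients, is expanded to at least 6 after one DLT, and needs at least 6 to be declared the MTD. That gives about 3-6 per level. Evaluable totals for three levels are:
- 6 + 6 + 6 = 18
- 6 + 6 + 3 = 15
- 6 + 3 + 3 = 12

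A pooled 18 therefore needs 6 at every level. Since 22 > 18, no level can hold 22, and no expansion cohort is described.

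**3. Precision.** For x survivors of n, the exact (Clopper-Pearson) 95% limits are L = BetaInv(0.025; x, n - x + 1) and U = BetaInv(0.975; x + 1, n - x). Follow-up to 2 years is assumed complete; censoring would widen every interval.

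| Setting | x/n | 95% interval | Width (points) |
|---|---|---|---|
| One level | 1/3 | 1-91% | 90 |
| One level | 1/6 | 0.4-64% | 64 |
| One level | 2/6 | 4-78% | 73 |
| Pooled | 5/12 | 15-72% | 57 |
| Pooled | 6/15 | 16-68% | 51 |
| Pooled | 7/18 | 17-64% | 47 |
| MTD level as assumed | 9/22 | 21-64% | 43 |

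The expected width at a true rate of 40%, averaged over the binomial distribution of x, is 84 points at n = 3, 71 at n = 6 and 46 at n = 18.

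**4. Against the plan's 20% and 40%.**
- True rate 40%, chance that L exceeds 20%: at n = 3 this needs 3/3, 0.4^3 = 6%; at n = 6 at least 4/6, 18%; at n = 18 at least 8/18, 44%.
- True rate 20%, chance that U falls below 40%: at n = 6 even 0/6 has U = 1 - 0.025^(1/6) = 46%, so the chance is zero, and likewise at n = 3. At n = 18 the largest count that works is 2/18 (U = 35%), and P(X <= 2) = 27%.

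Pooling raises both chances, but even at the maximum of 18 each stays below one half.

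**The case against.** The strongest reply has four parts.

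- **The plan concedes the imprecision.** The objective is worded as preliminary, and Section 15.1 cites small size and lack of power and declines to use the survival benchmark as a decision rule. This stands and limits the weight of the point. It does not supply the missing overall rate or its interval.
- **Dose-specific rates are natural in a dose-escalation trial.** A pooled rate averages 3 x 9 = 27 Gy to 3 x 11 = 33 Gy and is not survival at the MTD. This also stands, which is why the pooled figure needs a label and the by-level listing should stay. The pooling for perfusion CT serves an association analysis, so it shows no inconsistency in itself. It does show that the section says so when it means to combine levels.
- **With 22 at the MTD, by-level analysis would be adequate.** 9/22 gives 21-64%, slightly narrower than 7/18. That is true, but the premise conflicts with the maximum of 18.
- **Pooling is not forbidden.** Section 13.2.1 assigns Kaplan-Meier estimation to PFS and OS without a dose split. A reader might infer that 15.1 permits by-level results only, but that rests on silence. What the text supports is that no pooled estimate is described.

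A reader might also infer that differences between levels will be presented as a dose comparison. No such comparison or test is planned. Section 18.0 mentions combining the data with a similar study elsewhere, but gives no sample size or method, so it does not fill the gap.

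**Conclusion.** The point holds as a modest, inexpensive improvement to a secondary and explicitly preliminary objective. By-level 2-year rates from 3-6 patients are close to uninformative, with widths of 64-90 points in the examples above. The objective as worded calls for an overall rate that Section 15.1 does not describe, and the 22 patients behind the survival benchmark cannot arise from 18.

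It is tempting to conclude that a pooled estimate would make the objective succeed. The figures do not support that: 5/12, 6/15 and 7/18 all give intervals containing both 20% and 40%. Nor should the 90 points for 1/3 be set directly against the 47 for 7/18, since a pooled 18 evaluable patients requires 6 at every level. With one or two levels at 3, the pooled widths are 51-57 points. The MTD level itself must have at least 6.

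A reader might extend the point to the quality-of-life tables, which are also laid out by level. Those are purely descriptive and no error is shown there.

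The figures assume complete 2-year follow-up, exact binomial intervals in place of Kaplan-Meier ones, and evaluable patients as the count. Treated patients who were not DLT-evaluable could add a little information on efficacy.

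**What to change.** In Section 15.1:

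1. Add pooled 2-year estimates over all patients who received SBRT, each with a 95% confidence interval: Kaplan-Meier for PFS and OS, and cumulative incidence for patterns of failure and for local control where competing risks apply. Label them as averaging 27-33 Gy and as preliminary.
2. Keep the by-level results as descriptive listings.
3. Reconcile the 22 patients at the MTD level with the maximum of 18. Either restate the survival benchmark for a number the design can deliver, or describe where the additional patients come from.

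The cost is a few sentences and one more set of estimates. If the benchmark is restated within 18, no new patients, visits or data are needed. The drawback is that the pooled rate mixes doses and does not estimate survival at the MTD, which the label must make plain.

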We will measure changes in the perfusion/permeability related parameters of peripancreatic small intestine before, during and after SBRT for LAPC using pCT and correlating these changes with the development of gastrointestinal toxicity such as duodenal ulcers, strictures, or enteritis. Patients will undergo baseline, post-first-fraction SBRT and post-treatment CT scans on the Siemens AS Open scanner in the Department of Radiation Oncology. Perfusion/permeability parameters reflect the rate of exchange of I and include K^{trans} (transfer rate of contrast agent between vascular space and extravascular and extracellular space (EES), v_e and v_p (volume fraction of EES and vascular space, respectively), F (blood flow at the capillary level), and τ (mean transit time across capillary) [68, 74]. These derived parameters will be measured at baseline and re-measured for comparison on post-treatment scans. Patients will be followed approximately every 3 months after SBRT. Follow-up evaluations will include history and physical with assessment for presence of late toxicity using NCI CTCAE v 4.0.

The region of interest (ROI) will be placed by an experienced radiologist on the entire tumor. Tumor margins will be evaluated by reviewing all prior imaging, including CT and possible conventional MR sequences (T1 and T2). For pancreas cancer, the actual tumor extent is unknown, especially after treatment, so the ROI placement will be inherently limited by interobserver variability, which can be studied on its own.

Data will only be analyzed if seen on functional images. ROI's will be placed on the entire tumor. Tumor heterogeneity will be addressed by measuring standard deviation and skewness of the derived metrics. The experienced radiologist will draw the ROI on the normal tissue. A physicist and radiologist will review the images being acquired together to ensure the same region ROIs are covered in pre and post treatment images. The results from the study will provide the minimum size deemed measurable for the derived metrics.

13.2.3 *To investigate vascular and cellular changes resulting from SBRT for LAPC using pCT derived parameters that can predict treatment response and to assess any correlation between these pCT derived parameters and local control and progression-free survival.*

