We will measure changes in diffusion and perfusion/permeability related parameters. Comparisons will be made between the pre-treatment, post-first-fraction SBRT and post-treatment pCT (K^{trans} , v_e and v_p , F , and τ) derived parameters. The baseline measurements as well as intra- and post-treatment changes in these parameters will be correlated to disease response of the primary tumor, as defined by RECIST 1.1 i.e. complete response (CR), partial response (PR), stable disease (SD) and progressive disease (PD). K^{trans} is a reproducible biomarker of response in cancers such as brain, prostate and breast tumors and has been comprehensively investigated. We expect similar results in this study. However, the other metrics derived from pCT are exploratory in nature.

Progression free survival and local control for LAPC patients treated with FOLFIRINOX followed by SBRT will be determined as described in 12.2.1. The clinical outcomes will be compared with finding on pCT. Each MRI biomarker outcome will be studied for potential association with local control and progression-free survival.

We will use ROI analysis with mean parameter values to see which measure correlates better with disease response. We will analyze heterogeneity using voxel based analysis by measuring the standard deviation and skewness.

13.2.4. *To evaluate Quality of Life (QOL) in terms of global QOL, physical symptoms, physical functioning and emotional well-being after induction chemotherapy and SBRT. Testing will be 14 days prior to SBRT, 10-12 weeks after SBRT, and 6 months after SBRT.*

The primary objective of the QOL study is to document the patient's experience of treatment for locally advanced pancreatic cancer by examining global QOL, physical symptoms, physical functioning and emotional well-being at baseline, during treatment, and after treatment. Subjects will be giving 2 questionnaires: (1) EORTC-PAN26 and (2) EORTC-QLQ-C30. The two questionnaires have a total of 56 questions, 54 out of which have answers on a scale of 1-4 and 2 questions have answers on a scale of 1-7.

QOL measures including EORTC-QLQ-C30[80] and the Pancreatic Cancer subscale (EORTC-PAN26)[81] will be assessed 14 days prior to SBRT (Time 0), 10-12 weeks

after SBRT (Time 1), and 6 months after SBRT (Time 2). The primary QOL endpoints include the EORTC global QOL, physical symptoms, physical functioning and emotional well-being.

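### Section 15.1 gives percent change from baseline as the only change scale for the pCT measures and does not exempt skewness, for which that scale fails when the baseline is negative or near zero.

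*Combined protocol and SAP*

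**What the plan says.** Section 15.1 sets one rule "For the two secondary objectives involving pCT parameters": it computes "all relative changes (i.e., percentage of change from the baseline", and "there will be two sets of changes, one based on the 90-minute CT and the other the 6-week CT". These changes are related to toxicity and to response at 6 months by logistic regression. For OS, LC and PFS, "survival analysis tools such as Cox model or Fine-Gray competing risks regression model will be used". Patients from all dose levels are pooled, and the design enrolls at most 18.

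Section 13 says what is measured. The listed pCT parameters are K^trans, v_e, v_p, F and tau. Section 13.2.2 adds: "Tumor heterogeneity will be addressed by measuring standard deviation and skewness of the derived metrics". Section 13.2.3, on tumor response, adds: "We will analyze heterogeneity using voxel based analysis by measuring the standard deviation and skewness". The same section also says: "The baseline measurements as well as intra- and post-treatment changes in these parameters will be correlated to disease response of the primary tumor". It describes the pCT metrics other than K^trans as exploratory.

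No section gives skewness a different change scale, or says what to do when a baseline value is zero or negative.

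**The concern.** Percent change needs a positive quantity with a meaningful zero. K^trans, v_e, v_p, F, tau and their standard deviations meet that condition. Skewness does not: it is a signed measure of asymmetry, and zero means only that the voxel distribution is symmetric. Dividing by a baseline of that kind makes both the direction and the size of the predictor depend on where the patient started, and not only on what SBRT did.

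With at most 18 pooled patients, a few reversed signs or one very large value can determine a fitted coefficient. What is at stake is whether the planned association between change in tumor skewness and response, LC, PFS or OS can be read as being about change at all.

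**Working it through.** The plan states no sample size, power or error rate for this analysis, so it has no figure to reproduce. The check has an algebraic part, which needs no assumption about the data, and a frequency part, which does.

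**Algebra.** With baseline B and follow-up F, percent change is P = 100 × (F − B) / B.

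- B < 0: P has the opposite sign to F − B.
- B = 0: P is undefined.
- B close to 0: P is unbounded.

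A rise of 0.25 from different baselines:

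| B | F | F − B | P |
|---|---|---|---|
| +0.50 | +0.75 | +0.25 | 100 × 0.25/0.50 = +50% |
| −0.50 | −0.25 | +0.25 | 100 × 0.25/(−0.50) = −50% |
| +0.05 | +0.30 | +0.25 | 100 × 0.25/0.05 = +500% |

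Opposite changes can also receive the same score. A rise from −0.5 to +0.5 gives 100 × 1.0/(−0.5) = −200%. A fall from +0.5 to −0.5 gives 100 × (−1.0)/0.5 = −200%.

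**Frequency.** The documents give no skewness values. Assumptions: baseline normal across patients with mean m and SD 0.5; true change normal with mean 0.25 and SD 0.25, independent of baseline; n = 18; 4000 simulated samples.

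- Share of patients with reversed sign = P(B < 0) = Φ(−m/0.5).
- Chance of at least one reversal among 18 = 1 − (1 − share)^18. For m = 0.5 this is 1 − (1 − 0.159)^18 ≈ 0.96; for m = 1.0 it is 1 − (1 − 0.0228)^18 ≈ 0.34.
- Rank correlation: median Spearman correlation, within samples of 18, between percent change and the true change.

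| Mean baseline m | Sign reversed | At least 1 of 18 reversed | Absolute percent change over 200% | Median rank correlation |
|---|---|---|---|---|
| 0 | 50% | about 100% | about 23% | about 0 |
| 0.3 | 27% | over 99% | 19% | 0.33 |
| 0.5 | 16% | about 96% | 14% | about 0.5 |
| 1.0 | 2% | about 34% | 3 to 4% | 0.83 |
| 1.5 | 0.1% | about 2% | under 1% | 0.92 |
| 2.0 | about 0% | about 0% | about 0% | 0.95 |

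The spread matters as well as the mean: with baseline SD 0.25 and mean 1.0, reversal is about 0% and the correlation is about 0.95.

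The absolute difference would score a correlation of 1, but only by definition, since it is the true change in this set-up. No clinical outcome was simulated.

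**Leverage.** Using ordinary linear-regression hat values, one patient holds leverage above 0.5 in roughly 60% to 77% of samples of 18 for mean baselines from 0 to 1.0. On the absolute-difference scale the figure is 3% to 4%. This indicates how a single near-zero baseline can dominate a fit; it was not tested in a logistic, Cox or Fine-Gray model.

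**The case against.** The strongest reply is that Section 15.1 never mentions skewness. It speaks of pCT parameters, and Section 13 lists those as K^trans, v_e, v_p, F and tau, treating skewness as a summary of them. Section 13.2.3 also puts the correlation of mean ROI values with response and the voxel-based heterogeneity analysis in separate sentences. On that reading the plan leaves the scale for skewness open. This stands in part: it is fair to say that 15.1 fails to exempt skewness, but not that it prescribes the transformation for skewness by name. The remedy is the same either way, because percent change is the only change scale the plan offers.

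Two stronger readings are tempting, and the documents do not support them.

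- A reader might infer that the bowel-toxicity objective is compromised, because Section 2.2 aims to "document changes in tissue perfusion kinetics and heterogeneity that predict for development of gastrointestinal toxicity" in normal small intestine. But Section 13.2.2 specifies standard deviation and skewness for tumor heterogeneity, and no section says that skewness will be computed for bowel.
- A reader might infer that every skewness result would be uninterpretable. That depends on baseline values nobody has stated. If they lie well above zero, percent change tracks the true change closely (0.92 at a mean of 1.5). Section 13.2.3 also plans to use baseline measurements as predictors, and baseline skewness in that role is untouched.

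It is also true that these analyses are secondary, that metrics other than K^trans are labelled exploratory, and that no formal decision rests on them.

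**Conclusion.** The point holds as a limited one. The arithmetic failure is certain wherever a baseline skewness is negative or near zero. That the rule covers skewness is an inference from 15.1 read with 13.2.2 and 13.2.3. How often the failure would occur cannot be known from the documents; under the stated assumptions it runs from half of patients to almost none, depending on the baseline mean and spread.

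The effect is confined to the exploratory change-in-skewness predictors, mainly for tumor response, LC, PFS and OS. The MTD determination is unaffected. So are the sign and meaning of percent change for K^trans, v_e, v_p, F, tau and their standard deviations. The correction is worth making because it costs almost nothing and avoids choosing a scale after extreme values have been seen.

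**What to change.** Add one sentence to Section 15.1. It should restrict percent change (or log ratio) to the positive parameters and their standard deviations, and define change in skewness as follow-up minus baseline at both the post-first-fraction and the 6-week scan.

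No new data, scans or patients are needed. The small downside is that change in skewness is reported in its own units, so its coefficients are not directly comparable with those for the percent-change predictors.

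### The perfusion CT models pool the dose levels without a dose term; if dose affects both perfusion and outcome, the association they report may only reflect dose

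*Combined protocol and SAP*

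**What the plan says.** Section 15.1 of the combined protocol and SAP sets out the pCT analyses.

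- The predictors are "all relative changes (i.e., percentage of change from the baseline, note that there will be two sets of changes": one from the scan after the first fraction, one from the 6-week scan.
- Toxicity and response are analysed at "6 months post-SBRT by logistic regression".
- For OS, LC and PFS, "survival analysis tools such as Cox model or Fine-Gray competing risks regression model will be used".
- On dose, the only statement is "For these two objectives all patients will be combined for statistical analyses".

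No dose covariate, stratum or by-dose display is named for these models, either there or in sections 13.2.2 and 13.2.3.

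The same section treats dose differently elsewhere. For the survival and local control objective it says "For the above efficacy secondary objective, patients at different dose levels will be examined separately", and toxicity and QOL are to be tabulated by dose level. The levels being pooled start at 9 Gy x 3, and "dose level 2 will be 10 Gy x 3 fractions and dose level 3 will be 11 Gy x 3 fractions".

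**The concern.** Dose is escalated by design, and both post-SBRT scans follow irradiation, so the assigned dose comes before both the predictor and the outcome. Section 3.1 rests the trial on dose per fraction damaging tumor vessels, and a search for an MTD presumes that dose drives toxicity. If both links operate between the levels opened, dose is a common cause. The pooled model would then credit perfusion with an effect that belongs to dose.

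What is at stake is the purpose of the imaging work. Section 3.2 hopes that early perfusion changes will one day guide individual dosing, and it motivates this with a liver example in which function varied among patients given the same dose. A marker that only reveals which dose was given cannot serve that purpose, and the planned models cannot tell the two apart. Section 18.0 also says that the data will be combined with those of a similar study for publication, so an unadjusted estimate could carry forward.

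**Working it through.** **Inputs from the plan.** There are three dose levels, with enrolment after a DLT to "achieve having at least 6 evaluable patients at that dose level". So 3 x 6 = 18, which matches "The maximum number of patients needed for this dose escalation design is 18". The plan's escalation table also reproduces. With p the toxicity rate and q = 1 - p, the probability of escalation is q^3 + 3pq^2 x q^3. At p = 0.20 this is 0.512 + 0.384 x 0.512 = 0.709 (plan 0.71). At p = 0.50 it is 0.125 + 0.375 x 0.125 = 0.172 (plan 0.17).

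**Inputs assumed.** The plan gives no effect size, test or alpha for the pCT models. Assumed here are the perfusion shift s per dose level (in within-dose SDs), the outcome rates by level, 6 patients per level and a two-sided 5% test. Within a dose level, perfusion change and outcome are independent.

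**Mechanism by hand.** Code the levels d = 0, 1, 2 in equal numbers, so Var(d) = 2/3. Let the perfusion change be X = s x d + e with Var(e) = 1, and let the outcome rate be p(d) with mean m. Then

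r = s x Cov(d, p) / sqrt[(1 + 2s^2/3) x m(1 - m)].

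For rates 10/30/50%, m = 0.30 and Cov(d, p) = (0 + 0.30 + 1.00)/3 - 0.30 = 0.133.

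- s = 1: r = 0.133 / sqrt(1.667 x 0.21) = 0.23
- s = 0.5: r = 0.0667 / sqrt(1.167 x 0.21) = 0.13
- s = 0.25: r = 0.0333 / sqrt(1.042 x 0.21) = 0.07

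If s = 0 or the rates are flat, r = 0. Both links are needed.

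**Simulation with a score test.** False-positive (FP) rates come from 6,000 simulated trials per setting. The ORs are large-sample values (150,000 patients) per overall SD of perfusion change.

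| Outcome rates | Shift | Pooled OR | Pooled FP | Adjusted OR | Adjusted FP |
|---|---|---|---|---|---|
| 20/20/20% | 1.0 | 1.00 | 0.053 | 0.99 | 0.064 |
| 10/30/50% | 0 | 1.00 | 0.054 | 0.99 | 0.065 |
| 10/30/50% | 0.25 | 1.16 | 0.062 | 0.99 | 0.068 |
| 10/30/50% | 0.5 | 1.34 | 0.088 | 0.99 | 0.067 |
| 10/30/50% | 1.0 | 1.68 | 0.165 | 1.00 | 0.061 |
| 10/20/35% | 1.0 | 1.48 | 0.092 | 1.00 | 0.062 |
| 20/50/80% | 1.0 | 1.97 | 0.279 | 0.99 | 0.063 |

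The last row is an OR of 4 per level (odds 0.25, 1, 4), which is 16-fold from level 1 to level 3.

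**Simulation with a likelihood-ratio test**, shift 0.5 to 1 SD per level, spurious OR per within-dose SD:

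| Dose effect on outcome, per level | Pooled FP | Adjusted FP | Spurious OR, pooled | Adjusted OR |
|---|---|---|---|---|
| OR 4 (logistic) | about 15-30% | about 10% | 1.5-1.8 | 1.0 |
| HR 0.5 (Cox) | about 12-25% | about 7% | - | - |
| OR 2 / HR 0.7 | about 8-13% | 7-10% | 1.2-1.35 (logistic) | 1.0 (logistic) |

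**Effect of 3+3 stopping.** When the toxicity outcome tracks DLTs, stopping limits how many levels are seen. At rates 20/50/80%, the plan's own table gives a probability of 0.71 x 0.17 = 0.12 that level 3 opens. Simulated under the 3+3 rule with a 1 SD shift, the pooled rate falls from 31% to 14%, against 9% adjusted, with a mean of 9 patients. At rates 10/31/64% and 1 SD it falls from 28% to 19%, against 8% adjusted; at 0.5 SD it is 13% against 10%. With OR 2 and 0.5 SD it is 10% against 11%, so adjustment gains nothing there.

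**Power cost of the dose term at n = 18.** For a true within-dose OR of 2 per SD, power is 0.25 adjusted and 0.21-0.25 pooled. For an OR of 3 it is 0.47 adjusted and 0.40-0.47 pooled.

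**The case against.** The strongest reply is that the documents do not establish a dose gradient over the range studied. Section 3.1 argues a threshold above 8 Gy per fraction, which the starting dose already passes. Nothing says that perfusion keeps changing from 9 to 11 Gy, and the first post-SBRT scan follows only one fraction, so its contrast is 9, 10 and 11 Gy, not the course totals. This stands, and it is why the size can only be given as a range.

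For bowel toxicity the dose link may be weak. Section 5.3 cuts the expanded bowel and stomach volumes out of the target, and sections 5.4 and 5.5 set absolute limits that do not vary by dose level and override coverage. Prescribed level may barely change bowel dose. This also stands. It shrinks the likely bias for toxicity, and it means that a dose-level term may not remove all of it.

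The likelihood-ratio test is itself inflated at this sample size, since it stays above 5% after adjustment. Only the gap between pooled and adjusted rates is due to dose. The bias in the estimate does not depend on the test.

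Finally, combining patients defines an analysis set and does not forbid a covariate. Section 13.2.3 calls the metrics other than K-trans exploratory, and no decision rule hangs on any of them. That limits the consequences, but leaves no adjustment pre-specified.

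**Conclusion.** The point holds for post-SBRT percent changes. The stated models are biased whenever dose affects both the perfusion change and the outcome, and the plan names nothing to separate the two. Under strong assumed effects the false-positive rate is about 15-30% (logistic) or 12-25% (Cox), against about 10% and 7% with a dose term, with a spurious OR of 1.5-1.8. That is an upper range. Weaker effects add a few percentage points at most, and a 0.25 SD shift adds little or nothing. The figures assume three levels of 6, and fewer or unequal groups are likely.

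A reader might infer more than this, and the documents do not support it:

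- That pooling is itself wrong. With at most 18 patients it is reasonable; the gap is the missing term.
- That the plan rules out adjustment. It is silent.
- That every pCT analysis is affected. The baseline values that section 13.2.3 also relates to response precede irradiation, so assigned dose cannot cause them.
- That a false association is to be expected. No dose effect on perfusion or outcome is quantified anywhere.

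The MTD decision is untouched. This is a cheap improvement to secondary analyses.

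**What to change.** In section 15.1, keep all patients combined and add:

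1. Dose level enters as one linear term in the logistic models (preferably with Firth's penalty, as events will be few) and in the Cox and Fine-Gray models, for all post-SBRT pCT changes.
2. The unadjusted estimate and a plot by dose level are shown alongside.
3. The results are labelled exploratory.
4. For the bowel-toxicity models, a statement that prescribed dose level is an imperfect proxy because normal-tissue limits override coverage, with a sensitivity analysis that uses the small-bowel dose section 3.1 already plans to correlate with toxicity.

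Do not stratify by dose instead: with 18 patients or fewer, even three equal strata hold at most 6 each.

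The cost is one degree of freedom, slightly wider intervals and a few sentences. Power at n = 18 is essentially unchanged. Specifying this now also avoids choosing the adjustment after the data are seen.
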